#### The seropositive or GMT population

The seropositive or GMT analysis population will include subjects who were seropositive at day 1 for a given HPV type. An increase in antibody titers pre- and postvaccination will be analysed for each of the 9 HPV types (6, 11, 16, 18, 31, 33, 45, 52, and 58). The seropositive analysis populations are HPV type-specific, i.e., each HPV type has its own seropositive analysis population. To be included in a particular HPV type-specific seropositive analysis population, subjects must:

- Have received all 3 vaccinations of the correct dose of GARDASIL®9 within acceptable day ranges (See Table 4).

- Have evaluable serology results at Day 1 and Month 7 based on serum samples collected within acceptable day ranges (See Table 5).
- Be seropositive to the appropriate HPV type at Day 1.
- Have no protocol deviations that could interfere with the evaluation of subject's immune response to GARDASIL®9.

#### **3.5.4.2 Safety Analysis Population**

The all subjects as-treated (ASaT) analysis population, comprised of subjects who received at least 1 dose of GARDASIL®9 and had at least 1 study visit with safety follow-up, will be the primary population for safety analyses.

### **3.5.5 Statistical Methods**

#### **3.5.5.1 Immunogenicity Analyses**

The primary analyses of immunogenicity will be conducted in the Per Protocol Immunogenicity (PPI) population as defined in Section 3.5.4.1. Immunogenicity data will be analysed separately for HIV and SOT patients. The potential influence of factors such as immunosuppressive therapy and time after transplantation for SOT patients and CD4-count and antiretroviral therapy for HIV patients will be estimated.

- Seroconversion

The primary outcome, seroconversion, defined as changing serostatus from seronegative at Day 1 to seropositive (antibody titre above seroconversion cut-off) by 4 weeks after Dose 3, will be described with 95% CI. Differences with historical controls will be determined with a test for binary (seroconversion or not) proportions.

- GMT

All titers will be log transformed and the antilog of the mean will be calculated to obtain the GMT. GMT will be described with 95%CI. GMTs of immunocompromised patients will be compared with GMTs of historical controls with a one sample *t*-test, comparing month 7 GMTs for each component.

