#### 1.4. Summary of study design

This is a single-center, open-label study on safety, tolerability and immunogenicity of Gardasil® in 18 to 45 year-old HIV patients, in 18 to 55 year-old solid-organ transplant (SOT) patients.

This study will enrol 100 HIV patients with CD4+ count of >200cells/mm^2 and 170 SOT patients, all of whom have not yet received a prophylactic HPV vaccine. The 170 SOT patients will be equally divided over 3 different SOT patient groups, namely heart, lung and kidney transplant patients. Therefore the target is to include approximately 57 heart transplant patients, 57 lung transplant patients and 57 kidney transplant patients. Enrolment in a SOT subgroup will be stopped when 57 patients have been included unless recruitment cannot be achieved within one of the other SOT-patient population.

All enrolled subjects will receive a 3-dose regimen (Day 1, Month 2, and Month 6) of GARDASIL®. Serum samples will be collected on Day 1 and Month 7 for anti-HPV 6, 11, 16, 18, 31, 33, 45, 52, and 58 antibody determination. The time point for comparison of immune responses will be Month 7, or approximately 4 weeks after the administration of the third dose. The safety/tolerability profile of the vaccine will be evaluated in all subjects in the study. Safety information will be collected on Day 1 through 1 month following the third vaccination or for a total of approximately 7 months for each subject.

The immunogenicity and the safety data will be analyzed per group of patients. More specifically a separate analysis of HIV and SOT patients is planned, since it is expected that the immunosuppressive therapy of SOT patients might have a more profound effect on immunogenicity following vaccination.

This study will provide a comparison of immunogenicity of Gardasil® in immunocompromised patients, with historical controls (15, 18). The number of subjects to be enrolled in the study was determined based on the primary immunogenicity objective.

---

 GARDASIL® (Human Papillomavirus 9-valent Vaccine, Recombinant) is a registered trademark of Merck Sharp & Dohme Corp., a subsidiary of Merck & Co., Inc., Whitehouse Station, New Jersey, U.S.A

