## 2.2 Objectives and hypothesis

### 2.2.1. Primary Objective Immunogenicity:

To determine the *immunogenicity* of Gardasil®9 with respect to HPV types 6, 11, 16, 18, 31, 33, 45, 52 and 58 in adult HIV (age: 18-45 years) and transplant patients (age: 18-55 years).

**Hypothesis:** GARDASIL®9 induces in 18-45-year-old **HIV patients** (>200 CD4 T cells/mm^2) seroconversion rates for HPV 6, 11, 16, 18, 31, 33, 45, 52, and 58 at 4 weeks after Dose 3 that are similar to those induced in historical controls (healthy persons between 18 and 45 years of age. If the proposed control data are not available, immunogenicity will be compared to data from male and female healthy persons between 18 and 26 years of age and previous data from the immunogenicity of Gardasil® in HIV patients). The seroconversion rate for each of the HPV types 6, 11, 16, 18, 31, 33, 45, 52, and 58 will be tested separately.

**Hypothesis:** GARDASIL®9 induces in 18-55-year-old **solid organ transplant patients** seroconversion rates for HPV 6, 11, 16, 18, 31, 33, 45, 52, and 58 at 4 weeks after Dose 3 that are similar to those induced in historical controls (healthy persons between 18 and 45 years of age. If the proposed control data are not available, immunogenicity will be compared to data from male and female healthy persons between 18 and 26 years of age). The seroconversion rate for each of the HPV types 6, 11, 16, 18, 31, 33, 45, 52, and 58 will be tested separately.

(Seroconversion is defined as changing serostatus from seronegative at Day 1 to seropositive (antibody titer above seroconversion cut-off) by 4 weeks after Dose 3)

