### **3.5 Statistical analysis plan**

This section outlines the statistical analysis strategy and procedures for the study. If, after the study has begun, but prior to database lock, changes are made to primary hypotheses, or the statistical methods related to those hypotheses, then the protocol will be amended (consistent with International Conference on Harmonisation [ICH] Guideline E-9). Changes to exploratory or other non-confirmatory analyses made after the protocol has been finalized, along with an explanation as to when and why they occurred, will be listed in the clinical study report (CSR) for the study. Post hoc exploratory analyses will be clearly identified in the CSR. All statistical analyses specified in this protocol will be conducted using R, version 3.0.2 (R Foundation for Statistical Computing, Vienna, Austria, 2013).

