**Table 6: Analysis Strategy for Safety Parameters**

Adverse Event Endpoint	Follow-Up Period		Summaries/Analyses			
	After Any Vaccination Visit		Any Time During Study	Incidence	Risk Difference and 95% CI (b)	p-Value
	Day 1 to Day 5 (a)	Day 1 to Day 15 (a)				
Clinical AE						

 
Any AE
 
Death
 
		•	•	•		

 
Injection-site adverse events (c)
 
						

 
Injection-site pain/tenderness, swelling, and redness
 
Other injection-site adverse reactions
 
Severe injection-site adverse reactions
 
Number (%) of subjects by maximum intensity rating, over all injection-site adverse reactions
 
Number (%) of subjects by maximum intensity rating, within each of the categories of injection-site adverse reactions
 
	•			•	• (d)	•
Systemic AEs						

 
Systemic AEs
 
Number (%) of subjects by maximum intensity rating, over all systemic AEs
 
		•		•	• (e)	
Temperatures						

 
Elevated temperatures (f)
 
Maximum temperatures (g)
 
	•			•	•	•

AEs of special interest						

 
• Serious AEs
 
• Serious VR AEs
 
• New medical conditions
 
		•	•	•	•	

(a) The day of vaccination is counted as Day 1.
 
(b) Defined as the difference in incidence between the comparison groups (SOT and HIV patients versus historical controls).
 
(c) For the injection-site redness and swelling 0 to 2.5 cm (0 to 1 inch) will be categorized as mild, >2.5 to 5 cm (>1 inch to 2 inches) will be categorized as moderate, and >5 cm (>2 inches) will be categorized as severe.
 
(d) Only for injection-site adverse reactions occurring in <math>\geq 1\%</math> of subjects in either group.
 
(e) Only for systemic AEs occurring in <math>\geq 1\%</math> of subjects in either group.
 
(f) Defined as maximum (over the follow-up period) temperature <math>\geq 37.8^\circ\text{C}</math>.
 
(g) Distribution of maximum temperatures over the relevant follow-up period.
 
AEs, adverse events; VR, vaccine-related.
						

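### The primary hypothesis is that seroconversion is similar to historical controls, but the only planned comparison is a test for differences, with no margin or decision rule

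*Combined protocol and SAP*

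**What the plan says.** - **Hypothesis (2.2.1).** For HIV and SOT patients separately, the vaccine is expected to give seroconversion rates "at 4 weeks after Dose 3 that are similar to those induced in historical controls". The section adds: "The seroconversion rate for each of the HPV types 6, 11, 16, 18, 31, 33, 45, 52, and 58 will be tested separately". That makes 9 types × 2 cohorts = 18 comparisons.
- **Method (3.5.5.1).** Seroconversion "by 4 weeks after Dose 3, will be described with 95% CI". The comparison with controls is one sentence: "Differences with historical controls will be determined with a test for binary (seroconversion or not) proportions". It does not say whether the control rate is a fixed value (one-sample test) or a sample with its own error (two-sample test).
- **Control (1.4, 2.2.1).** The design summary compares results "in immunocompromised patients, with historical controls (15, 18"). Section 2.2.1 names healthy persons aged 18 to 45, with a fallback: "If the proposed control data are not available, immunogenicity will be compared to data from male and female healthy persons between 18 and 26". For HIV patients the fallback also includes earlier Gardasil data in HIV patients. No control rate or control size is stated.
- **Sample size (3.5.6).** The justification for seroconversion is the precision of the patients' own rate. The only powers quoted are for GMTs.
- **Safety (Table 6).** The plan does specify a risk difference with a 95% CI against controls here: "Defined as the difference in incidence between the comparison groups (SOT and HIV patients versus historical controls").

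**The concern.** A test for differences takes equality as its null hypothesis. A significant result is evidence against similarity. A non-significant result is only absence of evidence, and it becomes more likely as the evaluable sample shrinks. As written, no result of the planned test could support the primary hypothesis.

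Section 3.9 commits the study report to a comparison with historical controls. Without a definition of similarity, a margin or a rule, the reading of that comparison is left until the data are known. The documents do not say that p > 0.05 will be read as similarity, but they name no other result that would support the claim. The rest of the plan is built for estimation, so the conflict lies between the wording of the hypothesis and the test attached to it.

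**Working it through.** **1. The plan's own precision figures.** Half-width = 1.96 × √(p(1−p)/n), with inputs from 3.5.6:

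| Cohort | n | p | Half-width | Stated |
|---|---|---|---|---|
| SOT | 170 | 80% | 6.01 | 6 |
| HIV, types 6/11/16 | 80 | 95% | 4.78 | 4.8 |
| HIV, types 6/11/16 | 80 | 99% | 2.18 | 2.2 |
| HIV, type 18 | 80 | 90% | 6.57 | 6.6 |

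All agree. The sample size is sound for estimating the patients' own rates. It does not address a comparison with controls.

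**2. How often the test would find no difference.** From the documents: n = 80 and true rates of 95-99% (types 6/11/16) and 90% (type 18). Assumed, because the documents are silent: a control rate of 99% or 98%, a control that is fixed or a sample of 250 or 1000, and two-sided 5%. The chance of non-significance is the sum of binomial probabilities over all outcomes with p > 0.05. The tests are the exact one-sample binomial test and the pooled two-sample z test, with and without continuity correction.

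| Control | True rate | Fixed control, exact | Uncorrected, 250 / 1000 | Corrected, 250 / 1000 |
|---|---|---|---|---|
| 99% | 95% | 23% | 43% / 28% | 55% / 40% |
| 99% | 97% | 57% | 74% / 62% | 84% / 74% |
| 99% | 99% (no deficit) | 95% | 97% / 96% | 99% / 98% |
| 98% | 95% | 63% | 69% / 58% | 77% / 68% |
| 99% | 90% | 1% | 5% / 2% | 9% / 3% |
| 98% | 90% | 9% | 16% / 8% | 22% / 13% |

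For SOT at the planned 80%, the test rejects equality with probability above 99.8%, both with all 170 evaluable and with an assumed 85.

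**3. One result that does not depend on the test version.** Suppose 78/80 (97.5%) in patients and an assumed 248/250 (99.2%) in controls.

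- p = 0.53 (corrected), 0.25 (Fisher), 0.23 (uncorrected) and 0.135 (one-sample against 99.2%). All are non-significant.
- Difference: 97.5 − 99.2 = −1.7 points. Newcombe 95% CI: −7.9 to +1.05.
- With a fixed control, the exact CI for 78/80 is 91.26% to 99.70%. Subtracting 99.2 gives −7.9 to +0.5.

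Either way, a finding of no difference leaves a deficit of nearly 8 points open.

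**The case against.** The strongest reply is that this is an estimation study in all but a few sentences. The objective is to determine immunogenicity, each rate gets a 95% CI, and the sample size rests on precision. That is right, and it is why rewording the hypothesis is the lightest remedy. It does not remove the defect, because 2.2.1 states hypotheses to be tested and 3.5.5.1 supplies a test that cannot support them.

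The error also affects only part of the primary analysis. The nine SOT comparisons would almost certainly reject at 80%, and HPV-18 usually would. The 95% row is the bottom of the planned range for types 6, 11 and 16. No HIV rate is planned for types 31, 33, 45, 52 and 58. This limits the practical size and stands.

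The control figures are assumptions, and the 98-99% rates need not apply to the HIV fallback comparator. The GMT comparison in 3.5.5.1 is one-sample, so a fixed control is at least as plausible for seroconversion. That version gives the lowest figure against a 99% control (23%) but still 63% against 98%.

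Lastly, if the control is fixed, the planned CI for the patients' rate, less the control rate, already is the CI for the difference. This also stands: in that case only the presentation and the rule are missing. The plan does not say that the control is fixed.

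**Conclusion.** The concern holds. The planned test can contradict the primary hypothesis but cannot support it, and nothing in the documents says what would. This follows from the text alone and needs no assumed figure.

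The size does rest on assumptions about control rate, control size and test version. For HIV types 6, 11 and 16 at n = 80 and a 99% control, a non-significant result would occur in 23-55% of studies at a true 95% and in 57-84% at a true 97%. For HPV-18 at 90% the range is 1-22% across both control rates. For SOT at 80% it is negligible. The data stay usable whatever is done, so this should be fixed but does not undermine the study.

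**What to change.** Amend the protocol. Section 3.5 requires this when, before database lock, "changes are made to primary hypotheses, or the statistical methods related to those hypotheses, then the protocol will be amended". It is best done before any Month 7 serology is seen.

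1. In 2.2.1, replace the similarity hypotheses with an estimation objective.
2. In 3.5.5.1, report for each type and cohort the seroconversion rate and its difference from control with a 95% CI. Use Newcombe or Miettinen-Nurminen if the control is a sample, or the one-sample CI minus the control rate if it is fixed. State which applies.
3. Fix which named source supplies the control rate and size for each type: references 15 and 18, or the 18-45 data with the stated fallbacks, including the HIV one.
4. State that a non-significant difference will not be interpreted as similarity.
5. If a similarity claim is kept, the sponsor should state and justify a non-inferiority margin per type in advance and judge each type by the lower CI limit.

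**Cost.** No extra patients, samples or data. With 250 controls at an assumed 99%, the expected Newcombe half-widths for the difference are 5.4 points (n = 80, 95%), 6.8 (n = 80, 90%) and 6.2 (SOT, n = 170, 80%), against the plan's 4.8, 6.6 and 6. The plan's figures are Wald intervals. On that basis, 1.96 × √(p(1−p)/n + 0.99 × 0.01/250) gives 4.9, 6.7 and 6.1, so the real loss is smaller still.

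**Downside.** Similarity may not be claimable. With a purely illustrative 10-point margin, a 99% control and n = 80, the chance of passing with 250 controls (fixed control in brackets) is 98% (99%) at a true 99%, 73% (78%) at 97%, 38% (43%) at 95% and 3% (4%) at 90%. For SOT at 80% it is about 0%.

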## **2.5. Study design and duration**

### **2.5.1. Study design summary**

This is a single-center, open-label study on immunogenicity and tolerability of Gardasil®9 in 18 to 45 year-old HIV patients, in 18 to 55 year-old solid-organ transplant (SOT) patients.

This study will enrol 100 HIV patients with CD4+ count of >200cells/mm^2 and 170 SOT patients, all of whom have not yet received a prophylactic HPV vaccine. The 170 SOT patients will be equally divided over 3 different SOT patient groups, namely heart, lung and kidney transplant patients. Therefore the target is to include approximately 57 heart transplant patients, 57 lung transplant patients and 57 kidney transplant patients. Enrolment in a SOT subgroup will be stopped when 57 patients have been included unless recruitment cannot be achieved within one patient population.

All enrolled subjects will receive a 3-dose regimen (Day 1, Month 2, and Month 6) of GARDASIL®9. Serum samples will be collected on Day 1 and Month 7 for anti-HPV 6, 11, 16, 18, 31, 33, 45, 52, and 58 antibody determination. The time point for comparison of immune responses will be Month 7, or approximately 4 weeks after the administration of the third dose. The safety/tolerability profile of the vaccine will be evaluated in all subjects in the study. Safety information will be collected on Day 1 through 1 month following the third vaccination or for a total of approximately 7 months for each subject.

The immunogenicity and the safety data will be analyzed per group of patients. More specifically a separate analysis of HIV and SOT patients is planned, since it is expected that the immunosuppressive therapy of SOT patients might have a more profound effect on immunogenicity following vaccination.

This study will provide a comparison of immunogenicity of Gardasil ®9 in immunocompromised patients, with historical controls (15, 18). The number of subjects to be enrolled in the study was determined based on the primary immunogenicity objective.

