#### **3.5.3 Analysis Endpoints**

##### **3.5.3.1 Immunogenicity**

The immunogenicity endpoints are:

- The cLIA GMTs to HPV 6, 11, 16, 18, 31, 33, 45, 52 and 58 at 4 weeks after Dose 3.
- The cLIA seroconversion percentages to HPV 6, 11, 16, 18, 31, 33, 45, 52 and 58 by 4 weeks after Dose 3.

A subject with a cLIA titre at or above the serostatus cutoff for a given HPV type (see Section 3.3) is considered seropositive for that type. Seroconversion is defined as changing serostatus from seronegative at Day 1 to seropositive, by 4 weeks after Dose 3.

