#### **3.5.5.2 Statistical Methods for Safety Analyses**

All subjects who received at least 1 dose of GARDASIL®9 and have safety follow-up data will be included in the analysis of safety.

Prevalence of safety measures will be described with 95% CI and will be compared to the prevalence in historical controls with a test for proportions. Regardless of incidence, all AEs will be summarized as frequencies and percentages by vaccination visit, and across all vaccination visits. Specific AEs for which summaries will be provided are identified in Table 6. Incidence is defined as (number of subjects

with the indicated endpoint divided by the total number of subjects with follow-up over the relevant period) × 100%. Confidence intervals (95%) and 2-sided p-values will be provided without adjusting for multiplicity. Treatment administration data will be summarized for including number of vaccine injections received. Imputation methods will not be used to replace missing safety data. Safety data for HIV patients and SOT patients will be analysed separately.

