### **3.5.6 Sample Size and Power Calculations**

Based on an expected seroconversion rate of 80%, a sample size of 170 transplant patients allows to estimate the proportion of protected transplant patients with precision (95% confidence interval) of  $\pm 6\%$  (10).

Furthermore, based on an expected seroconversion rate 85-91%, a sample size of 140 HIV-patients allows to estimate the proportion of protected patients with precision (95% confidence interval) of  $\pm 6\%$  and 5% respectively (7). Based on expected differences in GMT to healthy populations, a sample size of 140 HIV-patients allows to estimate the GMTs HPV type 6, 11, 16 and 18 with a power of 0.38, 0.82, 1 and 1, respectively (7, 19).

Due to difficulties in the recruitment of HIV patients without genital warts a recalculation of the sample size was done. With a total sample size of  $n=100$ , a majority of whom will have no history of HPV-lesions, we expect to be able to use the data of at least 80 patients for the analysis seroconversion of each HPV type under study. Seroconversion rates of 95-99% for HPV types 6, 11 and 16 can then be

estimated with a margin of error of  $\pm 4.8\%$  -  $2.2\%$ , and the anticipated seroconversion rate of 90% for HPV type 18 with a margin of error of  $\pm 6.6\%$ .

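### The one-sample t-test of Month 7 GMTs treats the historical-control GMT as a known constant, so its p-values are too small

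*Combined protocol and SAP*

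**What the plan says.** Section 3.5.5.1 first defines the summary: "All titers will be log transformed and the antilog of the mean will be calculated to obtain the GMT", and "GMT will be described with 95%CI". It then fixes the comparison: "GMTs of immunocompromised patients will be compared with GMTs of historical controls with a one sample" *t*-test at Month 7 for each component. It gives no significance level or sidedness for this test. Two-sided p-values without multiplicity adjustment are mentioned only under safety, in section 3.5.5.2.

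The controls are people studied elsewhere. Sections 1.4 and 2.5.1 cite two 9-valent vaccine trials. Section 2.2.1 names healthy persons aged 18 to 45, with persons aged 18 to 26 as a fallback, and for the HIV cohort also earlier vaccine data in HIV patients. The documents give no control sample size, log-titre SD or confidence interval.

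GMT is a listed endpoint in section 3.5.3.1: "The cLIA GMTs to HPV 6, 11, 16, 18, 31, 33, 45, 52 and 58 at 4 weeks after Dose 3". Section 3.5.6 gives GMT power for the HIV cohort, introduced by "Based on expected differences in GMT to healthy populations".

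The analysis set is less clear. Section 3.5.5.1 puts the primary immunogenicity analyses in the per-protocol (baseline-seronegative) population. Section 3.5.4.1 gives the GMT name to a different set: "The seropositive or GMT analysis population will include subjects who were seropositive at day 1 for a given HPV type".

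**The concern.** A one-sample *t*-test is valid against a fixed reference value. Here the reference is a sample mean on the log scale. The difference between patient and control mean log titre has variance equal to the patient SE squared plus the control SE squared, and the planned test keeps only the first term. The denominator is too small and the p-value too low, for all nine types in both cohorts.

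The consequence is that a patient-versus-healthy GMT difference could be reported as significant when it lies within the sampling error of the control estimate. A test is named and power was calculated for it, so the p-values are likely to be read as evidence. The stated hypotheses concern seroconversion, and those conclusions do not depend on this test.

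**Working it through.** **Inputs**

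- Patients, n: 80 HIV patients evaluable per type (stated for seroconversion in section 3.5.6) and 170 SOT patients (planned enrolment). An intermediate SOT value applies the HIV evaluable fraction as an assumption: 0.80 × 170 = 136.
- Controls, M: not in the documents. Assumed range 250 to 2000, with 5000 as a further check.
- Level: two-sided 5%, assumed because none is stated for GMT.
- Log-titre SDs: equal in patients and controls, relaxed below.

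**The plan's own figures.** The stated GMT power (0.38, 0.82, 1 and 1 for types 6, 11, 16 and 18 at n = 140) cannot be reproduced, because no GMTs, SDs or control sizes are given. The precision figures in section 3.5.6 do reproduce with 1.96 × √(p(1−p)/n): 6.01 points for n = 170 at 80% (stated 6); 5.91 and 4.74 for n = 140 at 85% and 91% (stated 6 and 5); 4.78, 2.18 and 6.57 for n = 80 at 95%, 99% and 90% (stated 4.8, 2.2 and 6.6).

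**True level of the planned test.** Under equal population GMTs, the true standard error of the difference is √(1 + n/M) times the one the test uses. Hence

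true level = 2 × P(T with n−1 df > t(0.975, n−1) / √(1 + n/M)).

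Worked cases with M = 250:

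- n = 80: √(1 + 80/250) = 1.149; 1.990/1.149 = 1.732; level 8.7%.
- n = 170: √(1 + 170/250) = 1.296; 1.974/1.296 = 1.523; level 13.0%.

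| Patients | M = 250 | M = 500 | M = 1000 | M = 2000 | M = 5000 |
|---|---|---|---|---|---|
| HIV, 80 | 8.7% | 6.8% | 5.9% | 5.5% | 5.2% |
| SOT, 136 | 11.4% | 8.2% | 6.6% | 5.8% | 5.3% |
| SOT, 170 | 13.0% | 9.0% | 7.0% | 6.0% | 5.4% |

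The level falls to 6% at about 910 controls for n = 80 and about 1,960 for n = 170.

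**Unequal SDs.** The ratio becomes √(1 + r²n/M), where r is control SD over patient SD. For n = 80 and M = 500, r = 0.75 gives 6.0% and r = 1.25 gives 7.9%.

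**Simulation** (normal log titres, 200,000 runs per setting, M = 250, 500, 1000, 2000). The one-sample test rejected in 8.7, 6.9, 6.0 and 5.5% of runs for n = 80, and in 12.8, 8.9, 6.9 and 5.9% for n = 170. Welch's test rejected in 4.9 to 5.0% throughout.

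**If the baseline-seropositive set were used.** The Amendment 1 rationale quotes seroprevalence of 13% to 45%. Applied to 100 HIV patients this is 13 to 45 per type, and the level is 5.5% to 7.0% with 250 controls and 5.1% to 5.5% with 1000.

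**The case against.** The strongest reply is that the effect may be trivial. The control trials may be large: with 5000 controls the level is at most 5.4% in the table. The 13.0% figure needs both a small control set and all 170 SOT patients evaluable. This stands as a limit on size. It does not rescue the method, because the control set is left open in section 2.2.1, and the relevant M is the number of controls with evaluable titres for that type in the chosen age group, not a trial's total enrolment.

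A second reply is that, taken as a test against a published GMT used as a fixed benchmark, the one-sample test holds its level. That is true, but section 3.5.6 frames the question as a difference from healthy populations, and no fixed benchmark is declared.

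Third, the comparison matters less than seroconversion. It has no hypothesis of its own, and the error favours declaring a difference while the stated hypotheses claim similarity. The stated GMT power covers only the HIV cohort, four types and the superseded n = 140. For types 16 and 18 the stated power of 1 implies that a difference is expected, so the null is not the planning case. All of this stands and limits the importance of the point.

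Fourth, differences in population, age and assay run between studies may outweigh sampling error. That also stands, but it is no reason to leave out a variance component that can be included.

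Finally, section 3.5.4.1 ties the seropositive set to the rise in titre from before to after vaccination, so the per-protocol set is the more natural reading for the control comparison. Its label still leaves the set worth naming.

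**Conclusion.** The point holds. As written, the test omits the sampling error of the control GMT, and its p-values for equality of population GMTs are too small for any finite control sample. The direction is certain; the size is not, because the documents give no control n or SD. Under equal SDs and an assumed two-sided 5% level, the excess is about 0.5 to 4 percentage points for 80 HIV patients and about 1 to 8 points for 170 SOT patients, over 2000 down to 250 controls. It is smaller still with several thousand. This should be corrected before analysis, but it does not threaten the primary seroconversion analysis.

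**What to change.** Replace the one-sample *t*-test sentence in section 3.5.5.1 with a two-sample Welch comparison of log titres:

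- Use individual control data where available. Otherwise recover the control standard error from the published interval, SE = (ln upper − ln lower) / (2 × t(0.975, M−1)), and use √(s²/n + SE²) as the denominator, where s is the patients' log-titre SD, with Welch–Satterthwaite degrees of freedom.
- Report the patient/control GMT ratio with 95% CI for each HPV type and cohort, and state the level and sidedness.
- Name the analysis set for this comparison and distinguish it from the baseline-seropositive set.
- State the control source and its n, and say that Welch adds control sampling error but does not remove between-study differences in population, age or assay run.

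The change to the text is one sentence plus these specifications, with little extra analysis. It does require individual control data, or type-specific control GMTs with CI and n for the chosen age group; the documents do not show whether these exist.

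The statistical price is a larger standard error. With 250, 500, 1000 and 2000 controls it rises by 15, 8, 4 and 2% for n = 80, and by 30, 16, 8 and 4% for n = 170. As an illustration, for an assumed difference of 0.2 SD and n = 170, normal-approximation power is Φ(0.2 × √170 − 1.96) = 74% when the control GMT is taken as known. With control error included, Φ(0.2/√(1/170 + 1/M) − 1.96) gives 52% with 250 controls and 71% with 2000. The higher figure treats the control GMT as known, so the gap is not a real loss of information.
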